3.6.2. Outliers

Outliers will be identified during the data management and data analysis process, but no sensitivity analyses will be conducted. All data will be included in the data analysis.

3.7. Data Handling Conventions and Transformations

In general, age (in years) on the date of the first dose of study drug will be used for analyses and presentation in listings. If an enrolled subject was not dosed with any study drug, the enrollment date will be used instead of the first dosing date of study drug. For screen failures, the date the informed consent was signed will be used for age calculation. If only the birth year is collected on the CRF, “01 July” will be used for the unknown birth day and month for the purpose of age calculation. If only birth year and month are collected, “01” will be used for the unknown birth day.

Non-PK data that are continuous in nature but are less than the lower limit of quantitation (LOQ) or above the upper LOQ will be imputed as follows:

- A value that is 1 unit less than the LOQ will be used to calculate descriptive statistics if the datum is reported in the form of “< x” (where x is considered the LOQ). For example, if the values are reported as < 50 and < 5.0, values of 49 and 4.9, respectively, will be used to calculate summary statistics. An exception to this rule is any value reported as < 1 or < 0.1, etc. For values reported as < 1 or < 0.1, a value of 0.9 or 0.09, respectively, will be used to calculate summary statistics.
- A value that is 1 unit above the LOQ will be used to calculate descriptive statistics if the datum is reported in the form of “> x” (where x is considered the LOQ). Values with decimal points will follow the same logic as above.
- The LOQ will be used to calculate descriptive statistics if the datum is reported in the form of “≤ x” or “≥ x” (where x is considered the LOQ).

The COBAS® AmpliPrep/COBAS® TaqMan® HCV Quantitative Test v2.0 was used to determine HCV RNA results in this study. The LLOQ of the assay is 15 IU/mL.

When the calculated HCV RNA IU/mL is within the linear range of the assay, then the result will be reported as the “<< numeric value>> IU/mL”. This result will be referred to in this document as the numeric result or as “≥ LLOQ detected” for categorical result.

When HCV RNA is not detected, the result is reported as “No HCV RNA detected” or “target not detected”. This result will be referred to in this document as “< LLOQ target not detected” or “< LLOQ TND”.

When the HCV RNA IU/mL is less than LLOQ of the assay, the result is reported as “< 15 IU/mL HCV RNA detected”. This result will be referred to in this document as “< LLOQ detected”.

The overall category of HCV RNA < LLOQ includes “< LLOQ TND” and “< LLOQ detected.”

For numerical HCV RNA data, values below LLOQ will be set to the LLOQ – 1 IU/mL (ie, 14 HCV RNA IU/mL). HCV RNA values returned as “target not detected” will also be set to LLOQ – 1 IU/mL.

For selected analyses, HCV RNA data (IU/mL) will be transformed to the logarithmic (base 10) scale (\log_{10} IU/mL).

Natural logarithm transformation will be used for plasma/blood concentrations and analysis of PK parameters. Plasma concentration values that are below the limit of quantitation (BLQ) will be presented as “BLQ” in the concentration data listing. Values that are BLQ will be treated as 0 at predose time points, and one-half the value of the limit of quantitation (LOQ) at postbaseline time points for determination of summary and order statistics.

The following conventions will be used for the presentation of summary and order statistics:

- If at least 1 subject has a concentration value of BLQ for the time point, the minimum value will be displayed as “BLQ.”
- If more than 25% of the subjects have a concentration data value of BLQ for a given time point, the minimum and Q1 values will be displayed as “BLQ.”
- If more than 50% of the subjects have a concentration data value of BLQ for a given time point, the minimum, Q1, and median values will be displayed as “BLQ.”
- If more than 75% of the subjects have a concentration data value of BLQ for a given time point, the minimum, Q1, median, and Q3 values will be displayed as “BLQ.”
- If all subjects have concentration data values of BLQ for a given time point, all order statistics (minimum, Q1, median, Q3, and maximum) will be displayed as “BLQ.”

Exposure parameters selected for statistical analysis will be natural log-transformed. PK parameters that are BLQ will be imputed as one-half LOQ before log transformation or statistical model fitting.

3.8. Analysis Visit Windows

3.8.1. Definition of Study Day

Study day will be calculated from the first dosing date of study drug and derived as follows:

- For postdose study days: Assessment Date – First Dosing Date + 1
- For days prior to the first dose: Assessment Date – First Dosing Date

Therefore, Study Day 1 is the day of first dose of study drug administration.

The last dose date for an individual study drug will be the end date on study drug administration eCRF for the record where the “subject permanently discontinued” flag is ‘Yes’.

If there are subjects for whom the date of last study drug is unknown due to the reason that the subject was lost to follow-up and not able to be contacted, the date of last dose will be estimated using the maximum of nonmissing study drug start or stop dates, visit dates and laboratory collection dates (posttreatment visits and unscheduled visits are not included).

3.8.2. Analysis Visit Windows

Subject visits might not occur on protocol-specified days. Therefore, for the purpose of analysis, observations will be assigned to analysis windows. Analysis windows are defined for HCV RNA, vital signs, safety laboratory, and electrocardiogram (ECG).

In general, the baseline value will be the last nonmissing value on or prior to the first dose date of study drug.

HCV RNA, vital signs, safety laboratory and ECG data collected up to the last dose date + 2 days are considered to be on-treatment data and HCV RNA, vital signs, safety laboratory and ECG data collected after the last dose date + 2 days are considered posttreatment data.

The analysis windows for on-treatment HCV RNA, vital signs, and safety laboratory data are provided in [Table 3-1](#). The analysis windows for on-treatment ECG data are provided in [Table 3-2](#).

Table 3-1. Analysis Windows for On-treatment HCV RNA, Vital Signs and Safety Laboratory Data

Nominal Visit	Nominal Day	Lower Limit	Upper Limit
Baseline	1	(none)	1
Week 1	7	2	11
Week 2	14	12	21
Week 4	28	22	35
Week 6	42	36	49
Week 8	56	50	63
Week 10	70	64	77
Week 12	84	78	≥ 85

Table 3-2. Analysis Windows for On-treatment ECG Data

Nominal Visit	Nominal Day	Lower Limit	Upper Limit
Baseline	1	(none)	1
Week 4	28	2	42
Week 8	56	43	70
Week 12	84	71	≥ 85

HCV RNA, vital signs, safety laboratory and ECG data collected after the last dose date + 2 days will be assigned to the posttreatment follow-up (FU) visits. Visit windows will be calculated from the last dose date (ie, FU Day = collection date minus the last dose date) as shown in [Table 3-3](#).

Table 3-3. Analysis Windows for Posttreatment HCV RNA, Vital Signs, Safety Laboratory and ECG Data

Nominal FU ^a Visit	HCV RNA			Vital Signs, Safety Laboratory and ECG Data ^b		
	Nominal FU Day	Lower Limit	Upper Limit	Nominal FU Day	Lower Limit	Upper Limit
FU-4	28	21	69	28	3	30
FU-12	84	70	146		NA	
FU-24	168	147	190		NA	

^a FU-x visit = posttreatment Week-x follow-up visit.

^b Vital signs and safety laboratory data will be summarized only for the FU-4 visit (up to 30 days after last dose).

3.8.3. Selection of Data in the Event of Multiple Records in an Analysis Visit Window

Depending on the statistical analysis method, single values may be required for each analysis window. For example, change from baseline by visit usually requires a single value, whereas a time-to-event analysis would not require 1 value per analysis window.

If multiple valid, nonmissing, continuous measurements exist in an analysis window, records will be chosen based on the following rules if a single value is needed:

- In general, the baseline value will be the last nonmissing value on or prior to the first dosing date of study drug, unless specified differently. If multiple measurements occur on the same day, the last nonmissing value prior to the time of first dosing of study drug will be considered as the baseline value. If these multiple measurements occur at the same time or the time is not available, the average of these measurements (for continuous data) will be considered the baseline value.
- For postbaseline values:
 - The record closest to the nominal day for that visit will be selected.
 - If there are 2 records that are equidistant from the nominal day, the later record will be selected.
 - If there is more than 1 record on the selected day, the average will be taken, unless otherwise specified.

If multiple valid, nonmissing, categorical measurements exist in an analysis window, records will be chosen based on the following rules if a single value is needed:

- For baseline, the last available record on or prior to the date of the first dose of study drug will be selected. If there are multiple records with the same time or no time recorded on the same day, the value with the lowest severity will be selected (eg, normal will be selected over abnormal for safety ECG findings).
- For postbaseline visits, if there are multiple records with the same time or no time recorded on the same day, the value with the worst severity within the window will be selected (eg, abnormal will be selected over normal for safety ECG findings).

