- i A window of ± 2 days is allowed for the treatment visits on weeks 1, 2, and 12. A window of ± 4 days is allowed for the treatment visits weeks, and 4-10. Subjects who cannot complete their study visit per the visit schedule should ensure they do not run out of study drug prior to their next study visit. Compliance is critical to ensure adequate drug exposure.
- j A window of ± 7 days is allowed for the post treatment visits.
- k The sample should be collected on Day 1 prior to dosing, but may be collected at any time during the study or at a separate post-study visit, if necessary.

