8.2.1.2. Safety

The primary analysis set for safety analyses will be the Safety Analysis Set which includes subjects who received at least one dose of study drug.

Treatment-emergent data will be analyzed and defined as data collected from the first dose of study drug through the date of the last dose of study drug plus 30 days.

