8.5. Safety Analysis

Safety will be evaluated by assessment of clinical laboratory tests, physical examinations, vital signs measurements, at various time points during the study, and by the documentation of AEs.

All safety data collected on or after the first dose of study drug administration up to 30 days after the last dose of study drug will be summarized according to the study drug received. Safety endpoints will be summarized as the number (proportion) of subjects with events or abnormalities for categorical data or as an 8-number summary (n, mean, standard deviation, minimum, Q1, median, Q3, maximum) for continuous data.

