7. SAFETY ANALYSES

Safety data will be summarized for subjects included in the safety analysis set. Summaries of safety data (treatment-emergent [TE] adverse events [AEs], TE maximum toxicity grades, changes from baseline in laboratory tests and vital signs parameters) will include all data collected on or after the first dose date of study drug through the last dose date of study drug plus 30 days for subjects who have stopped the study drug.

All safety data (except for laboratory tests with results that were cancelled by the lab) will be included in data listings based on the Safety Analysis Set.

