7.2. Laboratory Evaluations

Laboratory data collected during the study will be analyzed and summarized using both quantitative and qualitative methods. Summaries of laboratory data will be provided for the Safety Analysis Set and will include data collected up to the last dose of study drug plus 30 days for subjects who have permanently discontinued study drug. The analysis will be based on values reported in conventional units. When values are below the LOQ, they will be listed as such, and the closest imputed value will be used for the purpose of calculating summary statistics as

specified in Section 3.7. Hemolized test results will not be included in the analysis, but they will be listed in by-subject laboratory listings.

A by-subject listing for laboratory test results will be provided by subject ID number and visit in chronological order for hematology, serum chemistry, and coagulation and other laboratory tests. Values falling outside of the relevant reference range and/or having a severity grade of 1 or higher on the Gilead Grading Scale for Severity of Adverse Events and Laboratory Abnormalities will be flagged in the data listings, as appropriate.

No formal statistical testing is planned.

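### Should the FU-4 window for vital signs, laboratory and ECG data run to Day 35, the last on-schedule day of the visit, instead of Day 30?

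*SAP*

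**What the plan says.** **Window.** SAP Table 3-3, titled "Analysis Windows for Posttreatment HCV RNA, Vital Signs, Safety Laboratory and ECG Data", gives FU-4 a nominal day of 28. HCV RNA has limits 21 to 69. Vital signs, safety laboratory and ECG data have limits 3 to 30, and FU-12 and FU-24 are marked as not applicable for them. Days count from the last dose. Footnote b reads "Vital signs and safety laboratory data will be summarized only for the FU-4 visit (up to 30 days after last dose". Its text leaves out ECG, but it is attached to the column heading that includes ECG.

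**Visit tolerance.** Protocol Table 6-2, footnote j (Section 6.1), and the same footnote in SAP Appendix 1: "A window of ± 7 days is allowed for the post treatment visits".

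**The 30-day rule.**
- Protocol 8.5 covers all safety data from first dose "up to 30 days after the last dose of study drug will be summarized according to the study drug received".
- Protocol 8.2.1.2 defines treatment-emergent data as running "through the date of the last dose of study drug plus 30 days".
- SAP 7 takes adverse event, toxicity grade and change-from-baseline summaries "through the last dose date of study drug plus 30 days for subjects who have stopped the study drug".
- SAP 7.2 says laboratory summaries "will include data collected up to the last dose of study drug plus 30 days for subjects who have permanently discontinued study drug".

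**Listings.** SAP 7 lists all safety data apart from laboratory results cancelled by the laboratory. SAP 3 sorts listings by subject and visit date. SAP 7.2 flags laboratory results in the listings: "Values falling outside of the relevant reference range and/or having a severity grade of 1 or higher".

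**The concern.** An analysis window normally covers at least the days on which its visit may be held. Here it does not. A subject who attends the Week 4 post-treatment visit on Day 33 has complied with the protocol. The HCV RNA sample from that day counts as FU-4, yet the hemoglobin, blood pressure and QTcF from the same day belong to no window.

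FU-4 is the only post-treatment visit at which these measures are summarised. Safety is a primary objective, and the cohort is planned at 15, so each such subject takes 1/15 = 6.7% off the FU-4 n. Read alone, a by-visit table would not show whether the missing subject came late within tolerance or did not come at all.

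**Working it through.** **1. The plan's own limits.** SAP 3.8.2 treats data to last dose + 2 days as on-treatment, so the first post-treatment day is 2 + 1 = 3, the stated lower limit. The upper limit of 30 is the last dose + 30 days of Protocol 8.5. Both limits are reproduced, so Day 30 is the safety cut-off carried into the window table, not a slip.

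**2. Overlap with the visit tolerance.** On-schedule days are 28 − 7 = 21 to 28 + 7 = 35, which is 15 days.
- Inside the safety window: Days 21 to 30, 10 days.
- Outside it: Days 31 to 35, 5 days; 5/15 = 33%.
- Inside the HCV RNA window (21 to 69): all 15.

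**3. Other visits.** The on-treatment windows of Table 3-1 contain their tolerances: for example, Week 2 is 14 ± 2 = 12 to 16 within 12 to 21, and Week 4 is 28 ± 4 = 24 to 32 within 22 to 35. So do HCV RNA at FU-12 (77 to 91 within 70 to 146) and FU-24 (161 to 175 within 147 to 190). FU-4 safety is the one exception among these, and the one window that meets the 30-day limit.

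**4. How many subjects.** The 33% is a share of calendar days, not of subjects, and the documents give no visit-timing data. Assume visit days follow a discretised normal centred on Day 28 and cut to Days 21 to 35, or are uniform over those days. Expected subjects = 15 × share.

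| Assumed timing | Share on Days 31–35 | Expected of 15 |
|---|---|---|
| SD 1 day | 0.5% | 0.1 |
| SD 2 days | 10.3% | 1.5 |
| SD 3 days | 19.8% | 3.0 |
| SD 4 days | 25.0% | 3.8 |
| SD 5 days | 27.9% | 4.2 |
| Uniform | 33.3% | 5.0 |

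**5. Which outputs.** From SAP Appendix 2, the by-visit tables that can carry an FU-4 row are:
- Laboratory: 15.11.6.1.1, 15.11.6.1.3 to .7, 15.11.6.2.1 to .6 and 15.11.6.3, so 1 + 5 + 6 + 1 = 13.
- Vital signs: 15.11.7.1.1 to .3, so 3.
- ECG: 15.11.9.2.1 to .4, so 4.

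The total is at most 13 + 3 + 4 = 20. ALT normalization by visit (15.9.2.6) has no window of its own. If it borrows the laboratory window it is affected as well; that is an inference.

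The same 30-day limit also keeps Day 31 to 35 laboratory values out of the treatment-emergent graded tables and their denominator (SAP 7.2.2.1, 7.2.2.2) and out of the counts of hemoglobin < 10 and < 8.5 g/dL (SAP 7.2.1). At present all these laboratory tables share one cut-off.

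**6. What Day 35 would do.** All 15 on-schedule days would be covered. Record selection under SAP 3.8.3 would still work against early samples: Days 21 to 35 lie at most 7 days from Day 28 and Days 3 to 20 at least 8, so an early-termination sample could not displace an on-schedule visit. There are two side effects:
- If a subject had one record on Days 21 to 30 and another on Days 31 to 35, the later would be chosen in 5 + 4 + 3 + 2 + 1 = 15 of the 10 × 5 = 50 day pairs, ties going to the later record.
- A hemoglobin of, say, 8.2 g/dL on Day 33 could be the FU-4 minimum in Table 15.11.6.1.1 yet be absent from the < 8.5 g/dL count in Table 15.11.6.1.2, unless the 30-day limit were moved there too.

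**The case for a change.** The best case for widening is that two purposes have been merged. Thirty days is a rule for attributing events to treatment, whereas a visit window exists to collect the visit. SAP 3.8.2 itself justifies windows on the ground that visits stray from their nominal days. One could use Day 35 for by-visit tables, keep 30 days for treatment-emergent summaries, and declare the difference in SAP 7.8. That needs no new data and only a few lines of text.

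Part of this stands: the window is narrower than the tolerance, and on-schedule visits can drop out of the FU-4 row. Three things weaken it:

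- Protocol 8.5 does not confine the 30 days to treatment-emergent events; it sets them for all summarised safety data. Routine adverse event collection ends at the same point (Protocol 7.3). The split would therefore be a departure from the protocol by a SAP that now conforms.
- The HCV RNA comparison carries little weight. An unbracketed missing value at SVR4 or SVR12 counts as failure (SAP 3.6.1), so that window has to be wide. A missing safety value only lowers n.
- A late visit and a missed one can be told apart outside the table. Listings carry dates, and SAP 4.1 counts subjects with no HCV RNA assessment from Day 21 onward. That count misses someone who skips FU-4 and returns later, but the listings do not, and with 15 subjects they are quickly read.

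**Conclusion.** No change to the plan is needed. The mismatch is real: Days 31 to 35, 5 of 15 permitted days, fall outside the FU-4 safety window. But the plan followed as written gives sound results under the protocol's own cut-off. The cost is a possible drop in n in one row of up to 20 descriptive tables, and perhaps in ALT normalization by visit. The size rests on assumed timing: about 0 to 5 of 15 subjects, with 5 only if visits are spread evenly over the whole tolerance. It may well be zero. SVR4, SVR12, SVR24, on-treatment summaries and adverse event tables do not depend on it, and no test is planned.

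Against that, Day 35 would break one shared 30-day limit into two and create values that appear in one laboratory table but not in its companion. Keeping Day 30 is a fair trade-off. ECG's absence from the wording of footnote b is clerical, since the column heading covers it. If several subjects do attend on Days 31 to 35, a note giving their number beside the FU-4 n in the study report would tell the reader all that is missing.

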4. SUBJECT DISPOSITION

4.1. Subject Enrollment and Disposition

A summary of subject enrollment will be provided for each country and for each investigator within a country, and overall. The summary will present the number and percentage of subjects enrolled. The denominator for the percentage calculation will be the total number of subjects in the Safety Analysis Set.

A summary of subject disposition will be provided. This summary will present the number of subjects screened, the number of subjects not enrolled, the number of subjects enrolled, and the number of subjects in each of the categories listed below:

- Safety Analysis Set
- FAS
- PK Analysis Set
- Completed study drug
- Did not complete study drug with reasons for premature discontinuation of study drug
- Completed study
- Did not complete the study with reasons for premature discontinuation of study

For the status of study drug and study completion and reasons for premature discontinuation, the number and percentage of subjects in each category will be provided. The denominator for the percentage calculation will be the total number of subjects in the Safety Analysis Set. Among subjects who completed study drug and who discontinued study drug, the number and percentage of subjects will be summarized for the following:

- Who had no HCV posttreatment Week 4 assessment and thereafter (No HCV FU-4 and thereafter)
- Who had HCV posttreatment Week 4 assessment but no HCV posttreatment Week 12 assessment and thereafter (With HCV FU-4 but No FU-12 and thereafter)

If a subject did not have any HCV RNA assessment \geq 21 days after the last dose of study drug (ie, lower bound of FU-4 visit for HCV RNA data), the subject is categorized as having “No HCV FU-4 and thereafter”. If a subject had the HCV FU-4 assessment but did not have any HCV RNA assessment \geq 70 days after the last dose of study drug (ie, lower bound of FU-12 visit for HCV RNA data), the subject is categorized as having “With HCV FU-4 but No FU-12 and thereafter”.

In addition, a flowchart will be provided to depict the disposition.

The following by-subject listings will be provided by subject identification (ID) number in ascending order to support the above summary tables:

- Subject disposition
- Reasons for screen failure (will be provided by screening ID number in ascending order)
- Lot number and kit ID

4.2. Extent of Study Drug Exposure and Adherence

Extent of exposure to study drug will be examined by assessing the total duration of exposure to study drug and the level of adherence to study drug specified in the protocol.

4.2.1. Duration of Exposure to Study Drug

Total duration of exposure to study drug will be defined as last dosing date minus first dosing date plus 1, regardless of any temporary interruptions in study drug administration, and will be expressed in weeks using up to 1 decimal place (eg, 4.5 weeks). If the last study drug dosing date is missing, the latest date among the study drug end date, clinical visit date, laboratory sample collection date, and vital signs assessment date that occurred during the on-treatment period will be used.

The total duration of exposure to study drug will be summarized using descriptive statistics and using the number (ie, cumulative counts) and percentage of subjects exposed through the following time periods: Baseline (Day 1), Week 1 (Day 7), Week 2 (Day 14), Week 4 (Day 28), Week 8 (Day 56), and Week 12 (Day 84).

Summaries will be provided for the Safety Analysis Set.

No formal statistical testing is planned.

